4.5 Randomization Procedures and Blinding

After informed consent or assent has been obtained from subjects, or legal parent/guardians or representatives, as applicable, screening procedures will be performed within 14 days of the scheduled start of the subject's HSCT conditioning regimen. Eligible subjects will be randomly assigned to receive DP 25 mg/kg/day in addition to BSC (DP arm) or BSC alone (BSC arm) in a 1:1 ratio. Randomization will be stratified according to risk of developing VOD (high-risk or very high-risk), age (>16 years or ≤16 years), and country using an interactive web response system (IWRS). Enrollment of those subjects meeting high-risk criteria will be capped at 65% of the total enrollment using IWRS.

This is an open-label study. To minimize potential for bias, the following blinding measures will be employed:

- The central reviewer of imaging studies will be blinded to study treatment assignment and all non-radiologic subject data (see protocol Section 6.3.1.2).
- Members of the EPAC will be blinded to study treatment assignment, will not be employees of the Sponsor, and will not be otherwise involved in the study (see protocol Section 6.3.1.3 and Section 11.9.2).

4.6 Determination of the Sample Size

On the basis of literature and results from a previously conducted prevention study (Study 2004-000592-33) with defibrotide (Corbacioglu et al. 2012), the proposed sample size for this study is 200 subjects per treatment arm for a total sample size of 400 subjects. Through simulations, it is shown that this sample size provides a 90% power to detect a hazard ratio (HR) of 0.46 for VOD-free survival by Day +30 post-HSCT in DP arm as compared with BSC arm, with an average of 68 events total. The HR of 0.46 is based on 86% and 72% VOD-free survival rates by Day +30 post-HSCT for DP arm and BSC arm, respectively, which translate to 14% and 28% as the incidence of VOD or death by Day +30 post-HSCT for the 2 arms, respectively. The assumptions for the simulations to calculate the sample size also include: (1) a 2-look group sequential design at 1-sided significance level of 0.025 (overall) with 1 interim analysis for efficacy stopping (1-sided significance level of 0.0005) or nonbinding futility stopping at ≤10% conditional power; and (2) 10% dropout rate.

4.7 Planned Interim Analyses and Reviews

Due to uncertainties associated with the study design assumptions, specifically the background rate of events in the BSC treatment arm and the size of the treatment effect, an interim analysis to be overseen by the DMC is planned when 70% of subjects are evaluated for the primary efficacy endpoint (ie, VOD-free survival by Day +30 post-HSCT), with specific rules for efficacy stop (ie, 1-sided alpha of 0.0005), futility stop (ie, conditional power <10%), and possible sample size re-estimation up to a maximum of 600 subjects total when the conditional power is in the promising zone. Details on the content of the interim analysis and adaptive design decision rules are provided in the interim Statistical Analysis Plan (iSAP) and specified along with the responsibilities of the DMC as part of the DMC charter.

4.8 DMC Safety Reviews

The independent DMC will also oversee periodic safety analyses. The periodic safety analyses will begin after 50 subjects have been randomly assigned to study treatment and monitored for a minimum of 3 months, and will occur approximately every 6 months thereafter.

5 CHANGES IN THE CONDUCT OF PLANNED ANALYSES

Three TEAEs of special interest (pulmonary hemorrhage, gastrointestinal bleeding, and hypersensitivity reactions) will be summarized. This is not specified in the protocol.

Section 10.1 clarifies censoring rules for subjects who don't undergo HSCT. The protocol defines the timing variable for these subjects but does not describe how these subjects who are not at risk of post-HSCT events should be censored.

Section 10.1 also added censoring rules for subjects who develop VOD prior to HSCT. This scenario is a possible outcome, albeit rare, and was not addressed in the protocol.

Section 8.2.1 clarifies how baseline is defined. The protocol defines baseline as follows: "Baseline/Study Day 1 is defined as the day before conditioning begins for patients randomized to the DP arm and the day that conditioning begins for patients randomized to the BSC arm." As the first dose of defibrotide is administered within 24 hours prior to the first dose of conditioning for subjects randomized to DP arm, the two definitions should result into the same Study Day 1 if the subjects strictly follow the protocol. In practice, it is possible that the subjects receive the first dose of defibrotide and then do not start conditioning on the next day. Thus, the definition in the protocol could result in a baseline assessment that occurs after defibrotide administration begins. For safety analyses, the baseline value should be the last assessment taken prior to study drug administration. For this reason, the definitions of Baseline/ Study Day 1 and of baseline values were further clarified in the SAP and this is the default definition used in the analyses.

6 STUDY ANALYSIS SETS

6.1 Screened Analysis Set

The Screened Analysis Set consists of all subjects who provided written informed consent and who undergo study screening procedures.

6.2 Intent-to-Treat Analysis Set (ITT)

The ITT Analysis Set will include all randomized subjects. This will be the primary analysis set for the primary efficacy endpoint and all other efficacy endpoints. Subjects will be analyzed by the treatment they were randomized to receive.

6.3 Modified Intent-to-Treat Analysis Set (mITT)

The mITT Analysis Set will include all randomized subjects who proceed to HSCT. This will be used in some of the sensitivity analyses. Subjects will be analyzed by the treatment they were randomized to receive.

6.4 Safety Analysis Set

The overall safety population will include all subjects randomized to the DP arm who receive at least 1 dose of defibrotide and all subjects randomized to the BSC arm. Subjects will be analyzed by the treatment they actually receive.

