#### **9.4 Analysis Populations**

The ITT population will include all randomized patients. This will be the primary analysis population for the primary efficacy endpoint and all other efficacy endpoints. The modified intent-to-treat (mITT) population will include all randomized patients who proceed to HSCT after randomization. The mITT population will be used in the sensitivity analysis of the primary efficacy endpoint and the key secondary efficacy endpoint.

The overall safety population will include all patients randomized to the DP arm who receive at least 1 dose of defibrotide and all patients randomized to the BSC arm.

The PK population will include patients who have evaluable PK data for the PK analyses.

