4.3.2.3 Other Secondary Endpoints

Other secondary efficacy endpoints will be tested without multiplicity adjustments, and nominal p-values will be reported. Other secondary efficacy endpoints include the following:

- Incidence of VOD by Day +30 post-HSCT
- VOD-free survival by Day +180 post-HSCT
- NRM by Days +100 and +180 post-HSCT

- Incidence of VOD-associated MOD (ie, severe VOD) by Days +30 and +100 post-HSCT (in those subjects who develop VOD)
- Proportion of subjects who have resolution of VOD by Day +180 post-HSCT and time to resolution of VOD
- Incidence of VOD after Day +30 post-HSCT up to Days +100 and +180 post-HSCT
- Health-related quality of life using EQ-5D-5L (adults only), EQ-5D-Y (proxy version 1; pediatric subjects 4 to 7 years of age), and EQ-5D-Y (self-report version 1; pediatric subjects 8 to <16 years of age)
- Pharmacokinetics of defibrotide
- Safety of defibrotide in addition to BSC vs BSC alone, including AE profile, SAE profile, laboratory abnormalities, and vital signs
- Incidence of Grades 2, 3, and 4 acute GvHD by Days +30, +100, and +180 post-HSCT, and the incidence of chronic GvHD by Day +180 post-HSCT
- Graft failure and time to neutrophil and platelet engraftment

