11.2 Adverse Events

Adverse events recorded in the case report form will be coded to SOC and PT using the MedDRA 19.1. The investigator will assess the relatedness of each AE to study drug. The severity of AEs will be recorded using the Common Terminology Criteria for Adverse Events (CTCAE 4.03).

At a minimum, for subjects in either the DP or BSC arm, the investigator must record all AEs and SAEs that occur from the time written informed consent is obtained until screen failure if applicable, or Day +60 post-HSCT, regardless of their relationship to study drug or procedure. Even if the minimum of Day +60 post-HSCT is met, the investigator must continue to record all AEs and SAEs that occur within 30 days after the last dose of defibrotide, regardless of their relationship to study drug or procedure. For subjects who do not receive HSCT, AEs must be collected for 70 days after Baseline or early termination, whichever occurs first. For subjects randomized but not treated, AEs will be collected for 70 days after randomization or early termination, whichever is earlier. Any SAE assessed as related to defibrotide or study procedures by the investigator should be reported regardless of time after study termination. Related SAEs reported after study termination will be collected in the Safety database only.

A treatment-emergent adverse event (TEAE) is defined as any event with onset date on or after the first dose of study treatment (either DP or conditioning regimen) or any ongoing event that worsens in severity after the date of the first dose of study treatment through the protocol-specific reporting period. Only TEAEs with the onset date on or before the end of the protocol-specific AE reporting period noted above will be included in summary tables unless otherwise specified. All AEs will be listed. For the purpose of calculating treatment emergence, incomplete onset dates will be imputed as detailed in Section [8.1.2.1](#).

AEs are graded by the investigator as Grade 1 (mild), Grade 2 (moderate), Grade 3 (severe), Grade 4 (life threatening), or Grade 5 (fatal). The severity grade of events for which the investigator did not record severity will be categorized as “missing” for tabular summaries and data listings, and will be considered the least severe for the purposes of sorting for data presentation.

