12 HOSPITAL RESOURCE UTILIZATION

Hospital resource utilization will be summarized by treatment arm for the Safety Analysis Set.

The duration of hospital stay in days will be calculated as follows:

$$\text{Days in hospital} = [\text{Date of hospital discharge}] - [\text{Date of hospital admission}] + 1$$

If hospital re-admission occurs during the study, the duration of each re-admission will be calculated as noted above and the number of days in the hospital across all admissions will be summed to obtain the total duration of the hospital stay for each subject. If the date of hospital admission is prior to the date of informed consent, the informed consent date will be used as the date of admission. If the subject is still in the hospital at the time of study completion, death, or early termination, the discharge date will be recorded as “Not Applicable” on the eCRF and the date of study completion/early termination/death will be used as the discharge date. The total duration of the hospital stay will be summarized. The number of subjects who were hospitalized prior to informed consent and the number who were still hospitalized at the end of study participation will be tabulated.

The total number of days in Intensive Care Unit (ICU) will be calculated using the same method noted above and summarized.

Inpatient resource use and/or use of diagnostic tests during the initial hospital stay or during any re-admissions will be summarized and listed including the following:

- Number of blood transfusions

- Total number of units for all transfusions received
- Total number of days of ventilator use
- Type of dialysis
- Total number of days on dialysis
- Number of liver biopsies
- Number of bone marrow biopsies
- Number of other biopsies

The following summary will be provided:

- Summary of hospital stay and resource utilization

The following listings will be provided:

- Listing of hospital and ICU stay
- Listing of inpatient resource utilization

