13 HEALTH-RELATED QUALITY OF LIFE

Health-related quality of life results will be summarized by treatment arm for the Safety Analysis Set.

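### The Safety Analysis Set removes DP subjects who were never dosed but keeps BSC subjects who never started treatment, and quality of life and hospital use are summarized on the same uneven set

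*SAP*

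**What the plan says.** SAP 6.4 includes "all subjects randomized to the DP arm who receive at least 1 dose of defibrotide and all subjects randomized to the BSC arm", and adds: "Subjects will be analyzed by the treatment they actually receive". Protocol 9.4 sets the same condition: DP patients need "at least 1 dose of defibrotide and all patients randomized to the BSC arm". The SAP therefore follows the protocol here.

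SAP 11.2 defines a TEAE as "any event with onset date on or after the first dose of study treatment (either DP or conditioning regimen"), or an ongoing event that worsens after that dose. SAP 8.2.1 sets the Baseline date at the earlier of the first defibrotide or conditioning dose, and SAP 8.3 starts the Prophylaxis Phase on that date.

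The set is also used outside safety. SAP 13: "Health-related quality of life results will be summarized by treatment arm for the Safety Analysis Set". SAP 12: "Hospital resource utilization will be summarized by treatment arm for the Safety Analysis Set". Neither section plans a repeat on ITT. SAP 6.2 says of ITT: "This will be the primary analysis set for the primary efficacy endpoint and all other efficacy endpoints". SAP 4.3.2.3 lists, among the other secondary efficacy endpoints, "Health-related quality of life using EQ-5D-5L (adults only), EQ-5D-Y (proxy version 1; pediatric subjects 4 to 7 years of age") and the self-report version for older children.

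**The concern.** The entry condition differs by arm: DP subjects need a dose, while BSC subjects need only randomization. The lack of a start of treatment in the control arm does not explain this, because SAP 4.4 starts BSC on the first day of conditioning.

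The plan expects some subjects to be randomized and never treated. SAP 8.2.2 has a rule for subjects with no dose of defibrotide or conditioning, SAP 11.2 has an AE collection rule for those randomized but not treated, and Protocol 7.1.2 describes removal of patients who lose eligibility when transplant is postponed. Such a BSC subject has no Baseline date, no Prophylaxis Phase and no possible TEAE, but still enlarges the BSC denominator. The DP counterpart disappears.

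A DP-randomized subject who is conditioned and transplanted without defibrotide received supportive care only. The as-treated sentence would place that subject under BSC, but the inclusion rule puts the subject in neither column.

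For quality of life and hospital use, the objectives (Protocol 2.2 and 2.3; SAP 4.2.2 and 4.2.3) are to compare the arms. The trial is open-label, so leaving before the first dose can depend on the assigned arm, and the one-sided removal need not be random.

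**Working it through.** The plan gives no figure for this point.

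**Inputs**
- N = 200 per arm (SAP 4.6). The accompanying power statement is not in dispute. With 68 events, HR 0.46 and 1-sided 0.02498, Φ(√(68/4) × |ln 0.46| − 1.9603) = Φ(3.202 − 1.960) = 0.893, close to the stated 90%. It rests on ITT, so the Safety set does not enter it.
- u, the share never treated: not given. Protocol 9.8.1 expects fewer than 2% of the ITT population not to reach HSCT. A BSC subject who never starts conditioning falls within that group, so about 2% is a planning ceiling for BSC if the share is the same in both arms. It does not bound undosed DP subjects, who could go without defibrotide and still be transplanted. I use u = 1% and 2%, equal in both arms, as an assumption.
- p, the event rate in treated subjects: 155/176 = 88.1% for any AE (Protocol 1.2) and 37/176 = 21.0% for hemorrhage (Protocol 1.3), both from the control arm of the earlier randomized prevention study. That study reports on all 176 controls, so these are illustrative values and not known treated-only rates.

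**Formulas**
- DP denominator = 200(1 − u); BSC denominator = 200.
- Reported BSC rate = p(1 − u); reported DP rate = p. Artificial gap = p × u.

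| | u = 1% | u = 2% |
|---|---|---|
| Denominators as written, DP / BSC | 198 / 200 | 196 / 200 |
| Denominators, one criterion in both arms | 198 / 198 | 196 / 196 |
| BSC any-TEAE rate (true 88.1%) | 0.8807 × 0.99 = 87.2% | 0.8807 × 0.98 = 86.3% |
| Gap | 0.9 points | 1.8 points |
| BSC hemorrhage rate (true 21.0%) | 0.2102 × 0.99 = 20.8% | 0.2102 × 0.98 = 20.6% |
| Gap | 0.2 points | 0.4 points |

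At 2%, the hemorrhage gap is worth 0.0042 × 200 = 0.8 of a patient.

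**Hospital use.** If untreated BSC subjects have almost no hospital days, the BSC mean is multiplied by (1 − u) and falls by about 1% to 2%.

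**Quality of life.** SAP 13.1.1 counts uncompleted questions and unknown change as categories, so untreated BSC subjects would alter the dimension percentages. EQ VAS means should hardly move, since these subjects would have few or no post-HSCT scores.

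**Does one-sided loss occur?** The earlier study reported AEs on 177 of 180 defibrotide patients (3/180 = 1.7% fewer) and all 176 controls. The protocol does not say why, and the figure says nothing about untreated controls.

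**The case against.** The strongest reply is that this is a pre-specified convention, identical in protocol and SAP, with a trivial effect. Only subjects who never start conditioning dilute the BSC rate; one who is conditioned but not transplanted can have a TEAE. AEs in untreated subjects are collected for 70 days and all AEs are listed. Quality of life and hospital use are descriptive, and moving them to ITT would mainly add missing entries. All of this stands, and it keeps the point minor. It does not justify a different entry condition in each arm when the SAP already has a common treatment start for Baseline and TEAEs.

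Three stronger readings are tempting and not supported:
- **That the rule hides harm.** The dilution lowers the BSC rate, so it disfavours defibrotide.
- **That the SAP plainly contradicts itself by taking an efficacy endpoint off ITT.** The list in SAP 4.3.2.3 also holds pharmacokinetics, safety, GvHD and engraftment. Protocol 9.8.3 omits quality of life from the secondary efficacy endpoints, SAP 10.2.2 does not cover it, and hospital use is exploratory. The heading is loose, so this is at most a supporting point.
- **That 2% is the expected never-treated share.** The figure is for no HSCT.

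**Conclusion.** The point holds as a minor one. The inclusion rule is uneven by its own wording, and it produces a one-directional distortion in BSC safety percentages and a one-sided exclusion from two comparisons between randomized arms. With 1% to 2% of BSC subjects untreated, any-TEAE rates shift by 0.9 to 1.8 points and hemorrhage by 0.2 to 0.4 points, making defibrotide look slightly worse. These sizes rest on an assumed untreated share, equal in both arms, and on event rates borrowed from the earlier study. A reader might infer a threat to the trial's main conclusions; there is none, because the primary and key secondary analyses use ITT.

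**What to change.** In SAP 6.4 and Protocol 9.4, use one criterion for both arms: all randomized subjects who receive at least one dose of defibrotide or of conditioning, analyzed by treatment actually received in the Prophylaxis Phase. A DP-randomized subject conditioned without defibrotide is then counted under BSC. In SAP 12 and 13, replace the Safety Analysis Set with ITT, by randomized arm.

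Asking for a defibrotide dose in DP and the start of conditioning in BSC would not be enough. SAP Section 5 foresees defibrotide being given without conditioning following the next day, and DP subjects conditioned without defibrotide would still be dropped. Even the common criterion need not give equal counts, because defibrotide starts before conditioning. It does ensure that everyone in a safety denominator has a Baseline date and can have a TEAE.

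The cost is a few sentences in the SAP, a minor protocol change (Protocol 11.6 requires a formal amendment), and some extra missing entries in the quality-of-life tables. SAP Section 3 requires analysis decisions to be made before database freeze, so this one should be too.

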6.5 PK Analysis Set

The PK Analysis Set will include all subjects who received at least one dose of defibrotide and had at least one evaluable defibrotide plasma concentration.

6.6 PK Evaluable Analysis Set

The PK Evaluable Analysis Set will include all subjects in the PK Analysis Set who have at least one evaluable defibrotide plasma PK parameter.

7 GENERAL CONSIDERATIONS

7.1 General Methods

The statistical principles applied in the design and planned analyses of this study are consistent with ICH E9 guidelines (ICH 1998).

Analysis datasets will be created according to Clinical Data Interchange Standards Consortium (CDISC) standards. SAS® version 9.3 (or higher) will be used to perform all data analyses and to generate tables, figures, and listings.

Summaries will order the treatment display from left to right as follows: DP (study treatment), BSC (control), and Total if a total column if applicable. Listings will include the randomized treatment arm, unique subject number, age, gender, and race. They will be sorted by treatment arm and then by subject number within treatment arm.

Unless otherwise specified, continuous data will be summarized using descriptive statistics comprising the number of subjects with data to be summarized (n), mean, standard deviation (SD), median, minimum (min) and maximum (max). Categorical variables will be presented using counts and percentages. Every category will be kept in the summary even if it has 0 subjects. Summary statistics of central tendency will be reported to one more decimal place than the collected data. Summary statistics of variability will be reported to one more decimal place than the commensurate measure of central tendency. For example, the mean and median for age will be reported to one decimal place because it is collected in full years. The standard deviation

of age will then be reported to 2 decimal places. P-values > 0.9999 will be presented as ' >0.9999 ' and p-value < 0.0001 will be presented as ' < 0.0001 '.

Subjects will be stratified at randomization according to country, risk of developing VOD (high risk or very high risk), and age (>16 years or ≤ 16 years). Analyses and summaries using the ITT and mITT analysis sets will be stratified using stratification data reported in the Interactive Response Technology (IRT) system at the time of randomization. Analyses and summaries using the Safety analysis set will be stratified using data reported in the Electronic Data Capture (EDC) system. If the number of subjects with discrepancies between IRT and EDC with regard to stratum assignment is greater than or equal to 5% of the randomized subjects, the primary and key secondary efficacy endpoint analyses will be repeated using the stratum assignment reported in EDC as sensitivity analyses. A listing of the discrepancies between IRT and EDC with regard to stratum assignment will be provided.

7.2 Multiple Comparisons and Multiplicity

The primary objective of the study is to compare the efficacy of DP in addition to BSC (DP arm) vs BSC alone (BSC arm) for the prevention of VOD as measured by VOD-free survival by Day +30 post-HSCT in subjects who are at high risk or very high risk for developing VOD. The study is designed with both an interim and a final analysis. To maintain an overall significance level at 1-sided alpha of 0.025, the incremental alpha is specified at 1-sided 0.0005 for interim analysis and 1-sided 0.0245 for final analysis (the corresponding nominal alpha is 1-sided 0.0005 for interim analysis and 1-sided 0.02498 for final analysis).

The key secondary objective of the study is to compare the efficacy of DP in addition to BSC (DP arm) vs BSC alone (BSC arm) for the prevention of VOD as measured by VOD-free survival by Day +100 post-HSCT in subjects who are at high risk or very high risk for developing VOD. To control the study-wise type I error, a sequential testing strategy will begin with the test on primary efficacy endpoint. If the test is significant, the test on the key secondary efficacy endpoint will be conducted at 1-sided alpha = 0.025. This gate-keeping approach will keep the family-wise error rate at 1-sided 0.025 for the comparisons of the 2 treatment arms in the primary and the key secondary efficacy endpoint analyses.

Other endpoints including secondary efficacy endpoints will be tested without multiplicity adjustments, and nominal p-values will be reported.

